6 STUDY PROCEDURES

6.1 Baseline Assessments

Subject and study partner/caregiver consent for the present study **must be** obtained prior to the final procedures being performed at the antecedent study's EOT or ET visit (if the study was ended early by the Sponsor) and before any new procedures are performed for the ACP-103-047 study. Data from the EOT/ET procedures of the antecedent study will be carried over to the ACP-103-047 study to be included as baseline information for the present study and this visit will be considered Baseline (Visit 1).

Study specific procedures are detailed below. All assessments will be completed according to the schedule described in [Table S-1](#). Every effort should be made to complete the required procedures and evaluations at the designated visits and times.

6.1.1 Medical History and Demographics

A complete medical and psychiatric history will be obtained from each potential subject at Baseline (Visit 1). Demographic information, including date of birth, gender, race, and ethnicity (if allowed by local regulations) will be recorded as well. Any new medical condition beginning after the informed consent form (ICF) has been signed will be captured as an AE. Subjects may be asked to provide pharmacy or medical records to substantiate the medication history.

6.1.2 Psychiatric, Dementia, and Neurological History

Details of the subject's psychiatric, dementia, and neurological history and treatment will be collected at Baseline (Visit 1).

6.2 Efficacy Assessments

6.2.1 Clinical Global Impression – Severity Scale

The CGI-S scale is a clinician-rated, 7-point scale that is designed to rate the severity of the subject's neuropsychiatric symptoms at the time of assessment using the Investigator's judgment and past experience with subjects who have the same condition (Guy 1976).

The CGI-S will be assessed at Baseline (Visit 1) and at all scheduled and unscheduled visits.

6.2.2 EQ-5D-5L

The EQ-5D-5L is a standardized instrument used as a measure of health outcome (Kind 1996). It measures 5 dimensions (mobility, self-care, usual activities, pain/discomfort, anxiety/depression) each of which has 5 potential responses. The responses record 5 levels of severity (no problems/slight problems/moderate problems/severe problems/extreme problems) within a particular EQ-5D dimension. The EQ-5D-5L Proxy version 1 will be used. For this version, a study partner/caregiver (the proxy) is asked to rate the subject's health-related quality of life in their (the proxy's) opinion.

The EQ-5D-5L will be assessed at Baseline (Visit 1) and at Weeks 12, 28, and 52.

6.2.3 Sleep Disorders Inventory

The Sleep Disorders Inventory (SDI) is an expanded version of one subscale of the Neuropsychiatric Inventory (NPI; Tractenberg et al. 2003). It consists of the 7 questions from the NPI sleep behavior domain. Each question includes a study partner/caregiver rating of frequency, severity, and study partner/caregiver distress with respect to the patient-participant sleep behavior for the 2 weeks prior to the visit. Thus, in contrast to a single rating for frequency and severity for all sleep disturbance-related behaviors, which would be incorporated into an overall NPI score, the SDI total score is derived after the study partner/caregiver rates the frequency and severity of each of the 7 separate sleep questions. Study partner/caregiver distress ratings are not part of the SDI total score, but distress is measured.

The SDI will be assessed at Baseline and at Weeks 12, 28, and 52.

6.3 Safety Assessments

6.3.1 Physical Examinations

A physical examination will be conducted at Baseline and at Weeks 28 and 52.

6.3.2 Vital Signs

Vital signs will include resting respiration rate, sitting systolic and diastolic blood pressure, pulse rate, and temperature and will be performed at all scheduled visits. The sitting blood pressure should be measured after the subject has been sitting for ≥ 3 minutes.

6.3.3 Weight

Weight will be reported (in kilograms) at all scheduled visits.

6.3.4 Electrocardiograms

All 12-lead electrocardiograms (ECGs) will be complete, standardized recordings. A single 12-lead ECG will be completed at all scheduled visits during the present study (Table S-1). All ECGs will be centrally read; the interpretation by the central cardiologist is considered the official interpretation. If a site performs additional ECGs beyond the single ECG prescribed at Baseline, the mean QTcF/QRS values of all the tracings of adequate quality will be used to determine eligibility.

At Baseline, a subject may be enrolled based on the machine read of the locally completed ECG. If the interpretation of the ECG by the central cardiologist indicates QTcF outside of the allowable range, the subject will be discontinued from the study, but this will not be considered a protocol deviation.

The subject must rest in a supine position before the ECG is obtained. ECG tracings (paper or electronic) will be reviewed and interpreted by a qualified clinician. ECG tracings and results (heart rate, RR, PR, QRS, QT, QTcF, and QTcB interval duration) will be included and summarized in the subject's study records.

6.3.5 Suicidal Ideation and Behavior

6.3.5.1 Columbia-Suicide Severity Rating Scale

The C-SSRS monitors changes in suicidal thinking and behavior over time, in order to determine risk (Posner et al. 2011). The following four constructs are measured: the severity of ideation, the intensity of ideation, behavior, and lethality.

The C-SSRS will be used to assess suicidal ideations and behaviors in subjects who are able to reliably complete the assessment, according to the judgment of the Investigator. Whether or not the subject can complete the C-SSRS should be documented in the eCRF for each subject at each visit. If the subject is not able to complete the C-SSRS, the GCAS should be used thereafter in the study to assess suicidality.

For subjects who completed the Baseline/Screening Version in the antecedent study and are still able to complete the C-SSRS assessment in the present study, the Since Last Visit

version will be administered at all visits. The C-SSRS results for each subject should be reviewed by the Investigator at each visit. If at any time the C-SSRS results for a given subject reveal potential suicidality, then the Investigator should assess the clinical significance of such results. If a clinically significant risk of suicidality is identified for a subject, then the Investigator should discontinue the subject and implement appropriate treatment ([Section 4.4](#)).

6.3.5.2 Global Clinician Assessment of Suicidality

The GCAS is a clinician-rated, 5-point scale that is designed to rate the subject's suicidality based on the report of the subject, the report of the study partner/caregiver, and the clinician's global assessment. Ratings can be 0 ("Absent"), 1 ("Feels life is not worth living"), 2 ("Wishes he/she were dead or any thoughts of possible death to self"), 3 ("Suicidal ideas or gesture"), or 4 ("Attempt at suicide"). The Investigator will record a subject rating, a study partner/caregiver rating, and a clinician rating.

If the GCAS was used in the antecedent study, suicidality since-last-visit will be assessed at Visit 1 (Baseline) and at all other visits.

If the subject is not able to reliably complete the C-SSRS at any point in the study in the Investigator's judgment, the GCAS will be administered and used thereafter in the study. The first assessment with the GCAS should assess lifetime suicidality and suicidality for the past 3 months and at all other visits, suicidality since the previous visit will be assessed.

As with the C-SSRS, if at any time the GCAS results for a given subject reveal potential suicidality, then the Investigator should assess the clinical significance of such results. If a clinically significant risk of suicidality is identified for a subject, then the Investigator should discontinue the subject and implement appropriate treatment ([Section 4.4](#)).

6.3.6 Mini-Mental State Examination

The Mini-Mental State Examination (MMSE) is a brief 30-point questionnaire that is used to quantitatively assess cognition ([Folstein et al. 1975](#)). The MMSE includes simple questions and problems in a number of areas: the time and place of testing, repeating lists of words, arithmetic, language use and comprehension, and copying a drawing. The MMSE is being used in this study to screen for cognitive impairment and as a safety measure.

The MMSE will be administered at all scheduled visits.

6.3.7 Extrapiramidal Symptom Rating Scale - Abbreviated

The Extrapiramidal Symptom Rating Scale (ESRS; [Chouinard and Margolese 2005](#)) was developed to assess drug induced movement disorders such as parkinsonism, akathisia, dystonia, and tardive dyskinesia with established reliability, validity, and sensitivity. It

consists of a questionnaire of parkinsonian symptoms, physician examination of parkinsonism, dyskinesic movements, and global impression of tardive dyskinesia. The ESRS-A, an accepted modified form of the original ESRS, will be used during the study to monitor for any worsening in extrapyramidal symptoms or signs at scheduled and unscheduled visits.

6.3.8 Laboratory Evaluations

Clinical labs are encouraged, but not required to be completed under fasting conditions. The laboratory evaluations will include, but are not limited to, the following:

Clinical chemistry serum tests

- Sodium (Na), potassium (K), chloride (Cl), phosphorus (P), calcium (Ca), carbon dioxide (CO₂), blood urea nitrogen (BUN), creatinine (CR), uric acid
- Alanine aminotransferase (ALT), aspartate aminotransferase (AST), gamma-glutamyl transpeptidase (GGT), alkaline phosphatase (ALP), total bilirubin (TBIL), lactate dehydrogenase (LDH)
- Glucose
- Albumin (ALB), total protein
- Prolactin
- Creatine kinase (CK)/creatinine phosphokinase (CPK)
- Lipid panel
 - Total cholesterol, HDL-cholesterol, triglycerides, LDL-cholesterol, very low density lipoprotein cholesterol

Pregnancy test

- A urine pregnancy test should be performed at all designated visits ([Table 6–1](#)) for women of childbearing potential
 - If urine cannot be obtained in women of childbearing potential, a serum pregnancy test should be done in its place

Hematology tests

- Complete blood count (CBC) including:
 - White blood cell (WBC) count
 - Absolute neutrophil count
 - Complete differential (relative and absolute)
 - Hematocrit (Hct), hemoglobin, red blood cells (RBC), platelets
 - Reticulocyte count

Urinalysis

- Blood, RBCs, WBCs, protein, glucose, ketones, specific gravity, pH, leukocyte esterase
- Reasonable efforts should be made to collect a urine sample from all subjects. Where collection of a urine sample proves impractical or impossible (e.g., because the subject is incontinent), failure to collect a urine sample should be recorded in the subject’s CRF, and will not be considered a protocol deviation

Urine toxicity screen

- Subjects who test positive for amphetamines are not eligible to participate in the study. Stimulants are prohibited per protocol during the study.
- Subjects who test positive for benzodiazepines, THC, or opiates may continue in the study and last usage should be noted at the study visit. In addition, restrictions listed in [Appendix A](#) should be followed.
- Reasonable efforts should be made to collect a urine sample at all scheduled visits as described in “Urinalysis” above

Laboratory evaluations will be completed according to the schedule presented in Table 6–1 and procedures detailed in the study Manual of Procedures. Additional safety testing may be performed at the discretion of the Investigator or designee.

Table 6–1 Safety Laboratory Evaluations

Visit	Tests
Visit 1 (Baseline)	CHEM, CBC, UA, urine toxicity screen, and urine pregnancy test ^a
Visit 5 (Week 12) and Visit 9 (EOT/ET)	CHEM, CBC, UA, urine toxicity screen
Weeks 2, 4, 8, 12, 16, 28, 40, and 52 (EOT/ET)	Urine pregnancy test ^a

Abbreviations: CBC=complete blood count; CHEM=clinical chemistry serum tests; EOT=end of treatment; ET=early termination; UA=urinalysis

^a To be completed only if female is of childbearing potential. If urine cannot be obtained in women of childbearing potential, a serum pregnancy test should be done in its place.

6.4 Safety Follow-up

A 30-day safety follow-up telephone call with the subject and study partner/caregiver is to be completed for subjects who complete the study as well as those who discontinue prematurely from the study. Subjects should have the following completed 30 (+4) days after last dose of study drug:

- Assessment of concomitant medications/treatments
- Assessment of AEs

6.5 **Unscheduled Visits**

Unscheduled visits may occur as determined by the Investigator. The following assessments generally should be recorded at each unscheduled visit: assessment of AEs, assessment of concomitant medications/treatments, measurement of vital signs, CGI-S, ESRS-A, C-SSRS (Since Last Visit version) or the GCAS if the C-SSRS cannot be completed. The Investigator may perform any additional safety evaluations deemed to be clinically indicated.

7 **ADVERSE EVENTS**

7.1 **Adverse Events**

Adverse events occurring after the first dose of open-label study drug in ACP-103-047 until safety follow-up assessment (conducted by telephone call) 30 days after the last dose of study drug, will be recorded as an AE in the ACP-103-047 study.

All ongoing AEs from the antecedent study (ACP-103-046) will be carried over and recorded from Baseline for the ACP-103-047 study until resolution or the follow-up safety assessment. All AEs must be either resolved or stable at end of study. If ongoing at the end of the study, the subject should be referred for appropriate treatment.

7.2 **Specification of Safety Parameters**

7.2.1 **Definition of Adverse Event**

An AE is defined as “any untoward medical occurrence associated with the use of a drug in humans, whether or not considered drug related” ([US FDA 2012](#)).

An AE can therefore be any unfavorable and unintended sign (e.g., an abnormal laboratory finding), symptom, or disease temporally associated with the use of a drug, without any judgment about causality or seriousness. An AE can arise from any use of the drug (e.g., off-label use, use in combination with another drug) and from any route of administration, formulation, or dose, including an overdose.

A suspected adverse reaction is any AE for which there is a reasonable possibility that the drug caused the AE.

AEs do not include the following:

- Stable or intermittent chronic conditions (such as myopia requiring eyeglasses) that are present prior to Baseline of the ACP-103-047 study and do not worsen during the study

- Medical or surgical procedures (e.g., surgery, endoscopy, tooth extraction, transfusion). The condition that leads to the procedure is an AE if not present at Baseline of the ACP-103-047 study.
- Overdose of concomitant medication without any signs or symptoms unless the subject is hospitalized for observation
- Hospitalization for elective surgery planned prior to study (situation where an untoward medical occurrence has not occurred)
- Pregnancy will not be considered an AE, but if it occurs, it will be reported on a pregnancy form

7.2.2 Definition of Serious Adverse Event

In addition to the severity rating, each AE will be classified by the Investigator as “serious” or “not serious.” The seriousness of an event will be defined according to the applicable regulations and generally refers to the outcome of an event. An SAE is one that meets one or more of the following:

- Is fatal
- Is immediately life threatening
- Results in disability or permanent damage
- Requires hospitalization
- Prolongs existing hospitalization
- Is a congenital anomaly or birth defect (in an offspring)
- Is medically significant

Definition of Life Threatening

A life threatening event places the subject at immediate risk of death from the event as it occurred. This does not include an AE, which, had it occurred in a more severe form, might have caused death.

Definition of Hospitalization

Hospitalization is defined by the Sponsor as a full admission to the hospital for diagnosis and treatment. This includes prolongation of an existing inpatient hospitalization.

Examples of visits to a hospital facility that do not meet the serious criteria for hospitalization include:

- Emergency room visits (that do not result in a full hospital admission)
- Outpatient surgery

- Preplanned or elective procedures
- Protocol procedures
- Social hospitalization, defined as admission to the hospital as a result of inadequate family support or care at the subject's primary residence

Definition of Disability or Permanent Damage

Disability is defined as a persistent or significant incapacity or substantial disruption of the ability to conduct normal life functions.

Definition of Medically Significant

Important medical events (medically significant events) that may not result in death, be life threatening, or require hospitalization may be considered to be an SAE when, based upon appropriate medical judgment, they may jeopardize the subject or may require medical or surgical intervention to prevent one of the outcomes listed in this definition. Examples of such events are intensive treatment in an emergency room or at home for allergic bronchospasm, blood dyscrasias, or convulsions that do not result in hospitalization or development of drug dependency or drug abuse.

An SAE may also include any other event that the Investigator or Medical Monitor judges to be serious or that suggests a significant hazard, contraindication, side effect, or precaution.

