14.1 Adverse Events

All AEs, classified by preferred term, will be coded using MedDRA version 23.0 or newer.

An AE (classified by PT) will be considered a TEAE if it started on or after the OL first dose of study drug and no later than the OL last dose date + 30. AEs reported on Day 1 based on pre-dose findings will not be considered as TEAEs.

For the following summaries, the event counts and the number and percentage of subjects reporting TEAEs will be tabulated by cohort and overall:

- TEAEs by SOC and PT
- Most frequently reported TEAEs by SOC and PT
 - PTs reported by $\geq 5\%$ and $\geq 2\%$ (overall) of subjects in the Safety Analysis Set
- TEAEs by PT
- TEAEs by SOC, PT, and maximum severity
 - if more than 1 AE occurs with the same PT for the same subject, the subject will be counted only once for that PT using the most severe occurrence
- TEAEs related to study drug by SOC and PT
- Treatment-emergent serious adverse events (TESAEs) by SOC and PT
- TEAEs leading to discontinuation of study drug by SOC and PT
- AEs with fatal outcome by SOC and PT
- TEAEs with fatal outcome (that occurred within 30 days of last dose) by SOC and PT

For tabulations that include SOC and PT the display will be sorted alphabetically by SOC and then by descending subject frequency for the PTs based on counts in the Safety Analysis Set within each SOC. SOCs will not be included in the TEAEs by PT tabulation. This display will be sorted by descending subject frequency based on counts in the Safety Analysis Set.

An AE listing by subject will display all events, including those which are not TE, and will include the verbatim term in addition to the MedDRA SOC and PT. This listing will also include all relevant eCRF data associated with the event: e.g. date of onset, dose level at date of onset, date resolved, date of the first and last dose of study drug, severity, frequency, outcome, relationship to study drug, action taken with study drug, and required therapy. When a date is presented, the study day associated with the date will also be displayed. Separate listings will be presented for subjects with SAEs, subjects with AEs leading to discontinuation and subjects who died (if any). In these listings, an indicator for TEAEs will also be included.

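### Section 7.2.2 exempts every elective procedure from the hospitalization criterion, without the pre-study limit in Section 7.2.1, so elective admissions for conditions that arise or worsen on open-label drug may be missed as SAEs

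*Protocol*

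**What the plan says.** Protocol Section 7.2.1 lists what is not an adverse event (AE). Three of its entries matter here.

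- An elective admission is exempt in this form: "Hospitalization for elective surgery planned prior to study (situation where an untoward medical occurrence has not occurred".
- Procedures are not AEs in themselves, but "The condition that leads to the procedure is an AE if not present at Baseline of the ACP-103-047 study".
- Stable or intermittent chronic conditions are left out only where they are "present prior to Baseline of the ACP-103-047 study and do not worsen during the study".

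Protocol Section 7.2.2 then defines when an AE is serious, with seven criteria. On the hospital criterion it states: "Hospitalization is defined by the Sponsor as a full admission to the hospital for diagnosis and treatment". A list follows under the lead-in "Examples of visits to a hospital facility that do not meet the serious criteria for hospitalization include", and one entry reads "Preplanned or elective procedures". That entry carries no qualifier.

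Protocol Section 9.5.1 places SAEs among the primary analyses. SAP Section 14.1 tabulates "Treatment-emergent serious adverse events (TESAEs) by SOC and PT" and adds no seriousness rule of its own. Protocol Section 7.5.2 requires SAEs to reach the sponsor or its designee within 24 hours of discovery.

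**The concern.** The two sections draw the elective exemption with different scope. Section 7.2.1 ties it to planning before the study and to the absence of an untoward event. The entry in 7.2.2 has neither condition, and because it is worded with an *or*, being elective is enough. The literal text therefore covers an admission scheduled in, say, month 6 for a condition that began in month 4 of open-label treatment.

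At stake are the completeness of the treatment-emergent SAE table and of 24-hour reporting, in a study whose stated rationale is to extend the safety database in adult and frail elderly patients. Approximately 100 sites apply the definition, so an entry open to two readings can also make classification differ between sites.

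**Working it through.** The documents state no figure on this point that could be reproduced. The check is a comparison of the text, followed by an illustrative bound.

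**1. Scope of the two exemptions**

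| | Section 7.2.1 | Section 7.2.2 entry |
|---|---|---|
| Question answered | Is it an AE? | Does the visit meet the hospitalization criterion? |
| When planned | Before the study | No limit |
| Cause | No untoward occurrence | No limit |

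**2. Does the 7.2.2 entry reach inpatient stays?** The same list has separate entries for outpatient surgery and for emergency room visits that do not end in full admission. Much of what the elective entry adds is therefore inpatient. The list also exempts social hospitalization, which it describes as an admission, so it is not confined to visits without one. The natural reading is that the entry carves an exception out of 7.2.2's own definition of hospitalization.

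**3. A worked case.** A condition begins after the first open-label dose and leads to a scheduled full admission.
- Under 7.2.1 it is an AE, because it was not present at Baseline.
- Under the 7.2.2 entry the admission does not make it serious.
- It is serious only if another route applies. The other criteria remain, including the medically significant one. So does the provision for events that the Investigator or Medical Monitor judges serious. The opening reference to applicable regulations also stands. The medically significant and judgment routes are worded permissively.
- If no route is used, the event is in the TEAE tables but not in the treatment-emergent SAE table, and the 24-hour rule is not triggered.

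**4. Worsened conditions.** The chronic-condition bullet in 7.2.1 withdraws its exemption when the condition worsens. Section 7.3.2.1 allows an AE to start on the date of a sustained worsening. The procedure bullet mentions only conditions absent at Baseline. It does not say *only if*, so it does not cancel the other two passages, but it is not aligned with them.

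**5. Illustrative bound.** The inputs are n = 750 (planned, approximate; SAP Section 3.5 says up to about 750) and two assumptions that the documents do not supply: the share q of subjects with such an admission over 52 weeks, and the true SAE proportion p.

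Subjects affected = 750 × q. SE of the percentage = √(p(1−p)/750).
- p = 10%: √(0.10 × 0.90/750) = 1.10 points
- p = 20%: √(0.20 × 0.80/750) = 1.46 points

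| Assumed q | Subjects | Shift/SE, p = 10% | Shift/SE, p = 20% |
|---|---|---|---|
| 0.5% | 3.75 | 0.46 | 0.34 |
| 1% | 7.5 | 0.91 | 0.68 |
| 2% | 15 | 1.83 | 1.37 |

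With the 353 rollover subjects of the second interim analysis (SAP Section 16.1), the p = 10% ratios fall to 0.31, 0.63 and 1.25.

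For each assumed q these are upper bounds. They suppose that no affected event is classified serious by another route and that no affected subject has another treatment-emergent SAE. The SE serves only as a yardstick, since no hypothesis test is planned.

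**The case against.** Four objections carry weight.

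- **The sections answer different questions.** Section 7.2.1 decides what is an AE, and 7.2.2 decides whether an AE meets one seriousness criterion. A reader might infer that they contradict each other, or that a site relying on 7.2.1 would call the event serious. Neither follows, because 7.2.1 contains no seriousness rule. This stands: the fault is misaligned scope and an open-ended entry in 7.2.2.
- **Only one of seven criteria is touched.** A reader might infer that these events necessarily drop out of the SAE tables and that the SAE rate is biased downward. The documents do not support that, given the remaining criteria and the judgment provision. They support *may be missed*. The fallbacks do not settle the matter, however, because they rest on case-by-case judgment beside a specific written exemption.
- **A milder reading exists.** The entry could cover only the procedure visit, leaving the underlying AE to be judged on whether it required hospitalization. That reading is possible, but the neighbouring entries on outpatient surgery and social admission make it the less natural one. Two defensible readings are themselves a reason to clarify.
- **The primary endpoint is TEAEs.** A new-onset event keeps its place in the TEAE tables, including those by maximum severity, so the primary endpoint is not undermined for such events. Only the seriousness flag is in doubt.

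A reader might also infer that 7.2.1 removes worsened Baseline conditions from AE recording. It does not: the chronic-condition bullet and Section 7.3.2.1 both point sites towards recording a worsening. What remains is an incomplete bullet.

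**Conclusion.** The point holds as a gap in scope. The elective entry in 7.2.2 has no limit on planning date or cause, and 7.2.1 shows that a narrower exemption was in view for the neighbouring question. Followed literally, it can leave an AE that required full admission classified as non-serious, outside the treatment-emergent SAE table and outside 24-hour reporting, unless another criterion or a judgment intervenes. Classification may differ between sites.

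The size cannot be estimated from the documents. The range of about 4 to 15 subjects rests on assumed admission rates of 0.5% to 2% in 750 subjects. It is a ceiling under each assumed rate, and no evidence that any event has been misclassified. The conclusion itself depends on the wording alone and justifies a clarification.

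**What to change.** 1. In Section 7.2.2, limit the elective entry to procedures planned before Baseline of ACP-103-047 for a condition that did not worsen during the study. This brings it into line with 7.2.1 and uses the Baseline anchor already found in that section.
2. In Section 7.2.1, extend the procedure bullet so that the underlying condition is an AE if it was not present at Baseline or worsened after Baseline. This matches the chronic-condition bullet and Section 7.3.2.1.
3. Send sites a memo explaining both changes.
4. Query AEs recorded as non-serious that are linked to an inpatient procedure. The schedule of assessments collects concomitant procedures at every visit, but the documents do not describe the form or say whether inpatient status is captured. The query can go only as far as those data allow.

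The cost is two wording changes, a memo, and modest site and data-management work. The reported SAE rate may rise slightly.
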